#### 7.5.2.3.4 Responses to individual task completion.

7.5.2.4 *Root causes of problems that occur while following the IFU:* an evaluation of the root causes of problems associated with user tasks, including but not limited to critical tasks, will be done through qualitative review of listings of *free form text* summarized in Sections 7.2.2 to 7.2.5 and 7.3.4.

7.5.2.5 The final secondary objective is to develop strategies to mitigate problems occurring while following the IFU. This does not have an associated statistical endpoint.

7.5.3 The exploratory endpoints are:  
[REDACTED]  
[REDACTED]  
[REDACTED]

#### 7.6 Analysis Dataset

7.6.1 There are three analytic datasets for this study:

7.6.1.1 Subject analysis file: CRF data

7.6.1.2 Laboratory test analysis file: including Epic, LIS and Laboratory Workbook data

7.6.1.3 Final Analysis file: Combining CRF and lab test data with variables required for analysis retained.

7.6.2 All subjects enrolled will be included in the analytic cohort.

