2 PROTOCOL SYNOPSIS

Primary Objective:	Determine the usability of the SARS-CoV-2 Specimen Collection Materials for at-home collection and mailing of sample to the testing laboratory
Study Design:	Prospective observational human factors usability study
Population:	Subjects of varying education levels, age, and health status
	Subjects are considered enrolled when they provide written informed consent.
	Approximately 30 subjects are targeted for enrollment.
Primary Endpoint:	The primary endpoint is the percent of samples from the fully enrolled cohort to return a valid SARS-CoV-2 test result (positive, not detected, or inconclusive). The target is 80% as an acceptable rate of success given the first-time task completion for minimally trained users.
Study Duration:	The study will be complete when approximately 30 self-collected nasal swab samples have corresponding SARS-CoV-2 test results (positive, not detected, inconclusive, invalid, or unable to be processed). Subject participation is up to one day from enrollment to completion.
Study Procedures:	Subjects will be observed while following the Instructions for Use (IFU) for the SARS-CoV-2 Specimen Collection Materials in a setting that simulates a home environment. Subjects will take the After-Scenario Questionnaire (ASQ) to measure ease of use. Subjects will have the opportunity to provide written feedback on their experience. Subjects will be asked questions about their comprehension of the IFU by the observer.

CONFIDENTIAL

May not be reproduced nor disseminated outside of Exact Sciences without permission

The specimens collected by the subject will be tested in the laboratory for SARS-CoV-2. Subjects will remain blinded to the results of the study sample.

Subject data will be collected and provided to the Sponsor.

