7 SUBJECT SELECTION AND WITHDRAWAL

Each subject must meet all the following inclusion criteria and none of the exclusion criteria to participate in this study.

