7.3 Subject Withdrawal

CONFIDENTIAL

May not be reproduced nor disseminated outside of Exact Sciences without permission

Subjects may be withdrawn from the study by any of the following mechanisms:

- Voluntary withdrawal of participation by the subject at any time during the study.
- Determination by the Investigator that it is in the best interest of the subject.
- Determination by the Sponsor it is in the best interest of the subject or study.
- Determination by review that the subject does not meet eligibility criteria.

All data available from enrollment to subject withdrawal will be collected. Data for the study visit will be collected for subjects who discontinue participation but who do not withdraw consent.

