8.2 Enrollment

Inclusion and exclusion criteria will be reviewed. After subjects have provided written informed consent, demographic information will be obtained, and subject eligibility will be confirmed.

Enrollment and the use of the device may occur on the same day.

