## 6. STUDY DESIGN

This study is a prospective observational human factors usability study designed to evaluate the IFU in the SARS-CoV-2 Specimen Collection Materials based on the successful completion of self-collection of a nasal swab sample, which includes a valid SARS-CoV-2 test result.

At the request of the FDA, subjects with a range of education levels and ages but without medical, laboratory, or COVID-19 specimen self-collection experience are being recruited. Study volunteers are pre-screened for highest education level attained and age group. The options for highest education level attained are: no high school; some high school; high school degree only; college degree; and advanced degree. Pre-screen age groupings are <18, 18-30 (early career), 31-45 (mid-career), 46-65 (later career), >65 (nearing retirement). Pre-screening for medical and laboratory experience is focused on identifying volunteers who have experience: collecting laboratory specimens in a medical setting; preparing specimens in a medical or laboratory setting; following a protocol in a medical or laboratory setting, e.g., for laboratory testing, R&D, and quality; or, who have been trained on any process or instrumentation in a medical or laboratory setting. Subject participation is up to one day from enrollment to completion.

[figure not shown]
Subjects are considered enrolled when they provide written informed consent. Subjects who provide informed consent are observed while following the IFU for the SARS-CoV-2 Specimen Collection Materials in a setting that simulates a home environment.

After following the IFU, subjects do the following: provide feedback on the usability of the IFU by completing a survey; answer comprehension questions; provide written feedback on the experience; and, address questions from the observer about problems during use. The observer is an employee of Exact Sciences.

The specimens collected by the subjects are tested in the laboratory for SARS-CoV-2. Subjects remain blinded to the test results.

Subjects' participation is considered completed following completion of the self-survey, forms, and potential interview with the observer or at the point of early termination. The study is considered complete when approximately 30 self-collected nasal swab samples have corresponding SARS-CoV-2 test results (positive, negative, inconclusive, or invalid).

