**Table 14. Demographic and Subject Characteristics, Overall and by SARS-CoV-2 Test Outcome**

	Overall	Valid SARS-CoV-2 Test Result	Invalid SARS-CoV-2 Test Result
Age, mean (SD)			
Age category, n (%)			
< 18			
18 to 30			
31 to 45			
46 to 65			
> 65			
Gender assigned at birth, n (%)			
Female			
Male			
Hispanic Ethnicity, n (%)			
Hispanic or Latino			
Not Hispanic or Latino			
Unknown			
Race, n (%) (subjects may report more than one option)			
American Indian or Alaska Native			
Asian			
Black or African-American			

	Statistical Analysis Plan: Usability Study of Home Collection and Mailing with SARS-CoV-2 Test Specimen Collection Materials (Protocol 2020-06)		
Doc. ID Number: [REDACTED]	Revision Number: 1.0	Effective Date: [REDACTED]	Page: 24 of 35

Native Hawaiian or other Pacific Islander			
White			
Unknown			
Education, n (%)			
No high school			
Some high school			
High school degree only			
College degree			
Advanced degree			
Medical or laboratory training, n (%)			
Yes			
No			
Prior experience with COVID-19 specimen self-collection, n (%)			
Yes			
No			
Previously had COVID-19 testing, n (%)			
Yes			
No			
Instructions for Use, n (%)			
Completed			
Discontinued			

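### The primary rate is calculated on everyone who consents, so a subject with an exclusion criterion who returns a valid sample counts as a success against the 80% target

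*SAP*

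**What the plan says.** **Enrolment.** The Protocol synopsis states: "Subjects are considered enrolled when they provide written informed consent". SAP 6 says the same.

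**Eligibility.** Protocol 7 requires that "Each subject must meet all the following inclusion criteria and none of the exclusion criteria to participate in this study". The exclusions in 7.2 are medical or laboratory training, earlier COVID-19 self-collection, and earlier SARS-CoV-2 testing. Protocol 8.2 opens by saying that the criteria will be reviewed, then continues: "After subjects have provided written informed consent, demographic information will be obtained, and subject eligibility will be confirmed". Appendix 1.0 lists consent first, then the demographics and exclusion form, then kit use.

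**Ineligibility found later.** One of the withdrawal routes in Protocol 7.3 is "Determination by review that the subject does not meet eligibility criteria". The same section says "All data available from enrollment to subject withdrawal will be collected".

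**Cohort.** SAP 7.6.2: "All subjects enrolled will be included in the analytic cohort". Protocol 9.4 agrees. SAP 8.1 calculates the primary frequency and percentage on the overall analytic cohort. Neither document makes an exception for ineligibility.

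**Pre-screen.** SAP 6: "Study volunteers are pre-screened for highest education level attained and age group". It goes on to describe pre-screening for medical and laboratory experience. It does not name the two COVID-19 exclusions.

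**Tables.** The Table 14 shell has Yes and No rows for each exclusion, for example "Prior experience with COVID-19 specimen self-collection, n" (%), split by valid and invalid result.

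**The concern.** The study has one arm and one headline number, a percentage read against 80%. Protocol 4.2.1 and SAP 7.5.1 justify that figure by the user being new to the task and barely trained. The exclusions in Protocol 7.2 are what make the subjects fit that description. If people who meet an exclusion stay in the calculation, part of the numerator comes from users to whom the justification does not apply. A trained or practised person is more likely to return an adequate swab, so the expected direction is upward.

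SAP 2 says the study report supports a regulatory filing, and SAP 6 says inexperienced subjects were recruited at the regulator's request. With about 30 subjects, one or two people can decide which side of 80% the reported figure falls on. If the rule is not fixed beforehand, someone must choose between two figures after seeing both.

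**Working it through.** **Inputs.** Target enrolment 30 (Protocol 9.1, SAP 8.7); target rate 80% (SAP 7.5.1). The documents give no inequality or confidence bound, so meeting the target is read here as a point estimate of at least 80%. The number of ineligible subjects is not given; one and two are assumed.

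**The plan's own figures.** The sample size of 30 rests on regulatory feedback and a precedent, with no error rate, power or null rate, so it cannot be reproduced by formula. The target can: 0.80 × 30 = 24 valid results.

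**Upward shift.** Let x of m eligible subjects have a valid result. Adding one ineligible subject with a valid result changes x/m to (x + 1)/(m + 1), a shift of (m − x)/[m(m + 1)].

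- One of 30: 23/29 = 79.3% (misses) becomes 24/30 = 80.0% (meets). Shift = 6/(29 × 30) = 0.69 points.
- Two of 30, both valid: 22/28 = 78.6% (misses) becomes 24/30 = 80.0% (meets). Shift = 1.43 points, or 0.71 each.
- At a higher rate the shift is smaller: 27/29 = 93.1% becomes 28/30 = 93.3%, or 0.23 points.

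These subjects have samples with results, so they count whether the denominator is subjects, samples or non-missing results.

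**How often the verdict would change.** With 30 enrolled in total, the first case needs exactly 23 valid among 29 eligible, and the second exactly 22 among 28. Binomial probabilities, given that the ineligible subjects are present and valid:

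| True rate among eligible | One ineligible: P(X = 23 of 29) | Two ineligible: P(X = 22 of 28) |
|---|---|---|
| 0.80 | 17.9% | 17.8% |
| 0.85 | 12.9% | 12.0% |
| 0.90 | 4.2% | 3.7% |
| 0.95 | 0.2% | 0.2% |

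The crossing also depends on the total, which the plan gives only as approximate. With 31 enrolled and one ineligible valid subject, the neighbouring cases are 23/30 = 76.7% against 24/31 = 77.4% (both miss) and 24/30 = 80.0% against 25/31 = 80.6% (both meet), so the verdict does not change. The upward shift itself remains.

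**Possible downward shift.** Suppose two consented subjects are found ineligible and never receive the kit, and 23 of the other 28 have valid results.

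- Denominator all enrolled (SAP 8.1): 23/30 = 76.7%, misses.
- Denominator samples (SAP 7.5.1) or non-missing results (SAP 8.5): 23/28 = 82.1%, meets.

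The Table 1 shell has rows for valid and invalid only, with no row for no result, so it does not settle which applies. One such subject cannot change the verdict when 30 are enrolled in total; two can.

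**The case against.** Analysing everyone enrolled guards against selective removal of failures, which matters when the observer is a sponsor employee (Protocol 8.1). Volunteers are pre-screened, so late-found ineligibility should be uncommon. All analyses are descriptive (SAP 8.6), so no type I error is affected. Table 14 shows how many subjects with each exclusion had valid results, and Listing 34 shows deviations by subject with the test result. All of this stands and limits the size of the problem. It does not remove it: Table 14 tabulates the three exclusions separately, so with overlap it only bounds the eligible-only rate, and nothing says which figure is to be read against 80%.

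Four stronger readings are tempting, and the documents do not support them:

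- **Subjects stopped before kit use certainly count as failures.** SAP 7.5.1, 8.1 and 8.5 point in different directions, so this is only possible.
- **The two COVID-19 exclusions are first asked after enrolment.** The pre-screen in SAP 6 does not name them, but Protocol 8.2 begins with a review of the criteria that could precede consent. Only confirmation is placed after consent.
- **Screen failures use up places, so fewer than 30 eligible users will be observed.** Protocol 14 counts enrolled subjects, but Protocol 5 and SAP 6 count samples with results. A screen failure without a sample takes no place under the second definition.
- **The Yes rows in Table 14 show that ineligible subjects are expected.** They tabulate form items collected from every subject (SAP 7.3.2).

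**Conclusion.** The point holds. Followed as written, the plan counts an ineligible subject with a valid sample as a success in the primary rate. Per subject the effect is small, about 0.7 points near 80% and less at higher rates. It changes the reading only when the eligible-only rate lies just below the target: given one such subject among 30, the chance is 17.9% if the true rate is 0.80 and 0.2% if it is 0.95. These figures assume one or two ineligible subjects, exactly 30 enrolled, and a point-estimate reading of the target. The downward shift, up to 5.5 points for two subjects (82.1% to 76.7%), depends on a denominator that the documents leave open. The rule should still be changed: the arm is not randomised, so keeping ineligible subjects protects no comparison, and excluding them on characteristics present before use, judged without knowledge of the result, introduces no outcome-dependent selection.

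**What to change.** 1. In SAP 7.6.2 and 8.1 and Protocol 9.4, calculate the primary rate on consented subjects who were given the kit and had no Protocol 7.2 exclusion present before using it. Apply this whenever the exclusion is discovered, provided that it is determined without knowledge of the test result.
2. Keep every such subject in the denominator whatever happens afterwards. Table 1 then needs a place for a subject who received the kit but has no result.
3. Report the all-enrolled rate beside the primary rate in Table 1, with the number ineligible. State that consented subjects never given the kit appear in disposition only.
4. Add the two COVID-19 questions to the pre-screen described in SAP 6.
5. Reconcile the target of about 30 between enrolled subjects (Protocol 14) and samples with results (Protocol 5, SAP 6).

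The cost is wording in both documents, two pre-screen questions, a line in Table 1 for the all-enrolled rate plus the entry in item 2, and possibly one or two more volunteers approached.

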### 8. STATISTICAL METHODS

#### 8.1 Primary Analysis

The primary endpoint will be summarized descriptively using frequency and percentage. These measurements will be calculated for the overall analytic cohort. The frequency and percentage (out of valid test results) of each valid lab result (positive, negative, inconclusive) will also be provided.

#### 8.2 Secondary Analyses

8.2.1 *Perceived usability of IFU:* A descriptive characterization of subjects' self-reported ease of use of the Specimen Collection Materials, as assessed by the ASQ, will be provided. This will be presented overall and by valid vs. invalid test result.

8.2.1.1 The mean, standard deviation, median, and interquartile range of the overall ASQ score will be calculated.

	Statistical Analysis Plan: Usability Study of Home Collection and Mailing with SARS-CoV-2 Test Specimen Collection Materials (Protocol 2020-06)		
Doc. ID Number: [REDACTED]	Revision Number: 1.0	Effective Date: [REDACTED]	Page: 12 of 35

8.2.1.2 The frequency and percentage of subjects with an overall score of 1 to 3 (indicating that the subject agrees to strongly agrees that they are satisfied) vs. 4 to 7 (indicating that the subject is neutral or strongly disagrees that they are satisfied) will be presented.

8.2.1.3 The frequency and percentage of each response to all three items will be presented. The denominator for the percentage across the mutually exclusive categories (responses 1 through 7, not applicable, and missing) will be the total number of enrolled patients.

8.2.2 *General comprehension of IFU:* A descriptive characterization of acceptable answers on general comprehension of the IFU will be provided. This will be presented overall and by valid vs. invalid test result.

8.2.2.1 The mean, standard deviation, median, and interquartile range of the total number of questions accurately answered will be calculated.

8.2.2.2 The frequency and percentage of total correct vs. incorrect responses will be presented.

8.2.2.3 The frequency and percentage of each response to all three questions will be presented.

8.2.3 *Problems associated with following the IFU:* A descriptive characterization of observer-reported problems associated with following the IFU will be provided overall and by valid vs. invalid test result.

8.2.3.1 The n, mean, standard deviation, median, and interquartile range of total number of tasks that the subject does not complete (as opposed to completes without issues or completes with issues or unexpected effort) will be calculated, overall and for the subset of fifteen critical tasks from the IFU. The frequency and percent of total problems in categories of 5-unit increments will also be reported. This will be presented for the subset of patients for whom the observer was able to observe the subject attempt all tasks. Subjects where the observer responded “not applicable” to one or more tasks will not contribute to this analysis.

8.2.3.2 The frequency and percentage of each observer-response to all 26 tasks will be presented.

8.2.3.3 Critical tasks will be explicitly labeled for easy identification.

8.2.4 *Root causes of problems that occur while following the IFU:* A qualitative evaluation of listings from the user reported data, external observer feedback on user interactions, and laboratory testing will be conducted by Clinical and Regulatory Affairs to assess the root cause of problems and evaluate mitigating solutions, e.g., whether specific parts of the IFU should be modified. The listings will be provided by Clinical Biostatistics to Clinical and Regulatory Affairs, presented by question within data stream. Critical tasks will be explicitly labeled for easy identification. Post-hoc analyses may be performed at the request of Clinical and Regulatory Affairs to help summarize their assessment of root cause issues.

8.2.5 The final secondary objective is to develop strategies to mitigate problems occurring while following the IFU. This does not have an associated statistical endpoint or quantitative analyses.

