### 7.2 Observer Collected Variables

- 7.2.1 After the observer provides the SARS-CoV-2 Specimen Collection Materials, which includes the IFU, to the subject, the observer records the following information by IFU task (check one): *subject completed step with no issues; subject completed step with issues or unexpected effort; subject did not complete step or required assistance; or, not applicable*, e.g., if the subject discontinued their participation. There are three sections to the IFU that contain a total of 26 steps for specimen collection and packaging. The three sections are summarized below, and the observer records a response for each task.
  - 7.2.1.1 *Before you collect*, which includes reading the instructions (one step) and preparing for collection (two steps).
  - 7.2.1.2 *Collect your nasal swab sample*, which includes twenty steps in total:
    - 7.2.1.2.1 preparing the tube label (two steps);
    - 7.2.1.2.2 opening nasal swab (two steps);
    - 7.2.1.2.3 removing the tube cap (four steps);
    - 7.2.1.2.4 swabbing nose (two steps);
    - 7.2.1.2.5 add swap to tube (two steps);
    - 7.2.1.2.6 removing swab from tube (two steps);
    - 7.2.1.2.7 replacing the tube cap (two steps);
    - 7.2.1.2.8 placing label on tube (one step); and,

	Statistical Analysis Plan: Usability Study of Home Collection and Mailing with SARS-CoV-2 Test Specimen Collection Materials (Protocol 2020-06)		
Doc. ID Number: 	Revision Number: 1.0	Effective Date: 	Page: 8 of 35

7.2.1.2.9 washing hands and adding [REDACTED] to bag (three steps).

7.2.1.3 *Ship your kit back to the lab*, which includes placing bag in bubble wrap (one step) and placing bubble wrapped bag in box (two steps).

7.2.2 The observer records *free form notes* during their observation of the subject while the subject is completing the IFU.

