7.5 Description of Study Endpoints

7.5.1 The primary endpoint is the percentage of samples from the fully enrolled cohort to return a valid SARS-CoV-2 test result (positive, negative, or inconclusive). The target is 80% as an acceptable rate of success given the first-time task completion for minimally trained users.

7.5.2 The secondary endpoints are:

- 7.5.2.1 *Perceived usability of IFU*: The subject's self-reported satisfaction and ease of using the IFU, assessed using the ASQ. The ASQ is a valid and reliable 3-item survey on user satisfaction associated with completing a task. Item response options are on a 7-point Likert scale where 1 = strongly agree and 7 = strongly disagree. An overall satisfaction score is calculated as the average of the non-missing responses to the items (theoretical range 1-7 with a lower score indicating higher satisfaction). Endpoints from the ASQ include:
  - 7.5.2.1.1 Overall score (*continuous*), where an average of 3.5 or lower on the overall ASQ score will be considered acceptable self-reported user satisfaction.
  - 7.5.2.1.2 Categorization of overall ASQ score as 1 to 3 (indicating that the subject agrees to strongly agrees that they are satisfied) vs. 4 to 7 (indicating that the subject is neutral or strongly disagrees that they are satisfied).
- 7.5.2.2 *General comprehension of IFU*:

	Statistical Analysis Plan: Usability Study of Home Collection and Mailing with SARS-CoV-2 Test Specimen Collection Materials (Protocol 2020-06)		
Doc. ID Number: [REDACTED]	Revision Number: 1.0	Effective Date: [REDACTED]	Page: 10 of 35

7.5.2.2.1 Total out of three questions accurately answered by subject when the observer evaluates the subject's comprehension of the IFU. The questions are summarized in Sections 7.2.3.1 – 7.2.3.3.

7.5.2.2.2 Responses to individual questions.

7.5.2.3 *Problems associated with following the IFU:*

7.5.2.3.1 The total number of tasks that the subject does not complete (as opposed to completes without issues or completes with issues or unexpected effort). The 26 tasks are summarized in Section 7.2.1.

7.5.2.3.2 The total number of critical tasks that the subject does not complete (as opposed to completes with no issues or completes with issues or unexpected effort).

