8.4 Demographic Analyses  
[REDACTED]

	Statistical Analysis Plan: Usability Study of Home Collection and Mailing with SARS-CoV-2 Test Specimen Collection Materials (Protocol 2020-06)		
Doc. ID Number: 	Revision Number: 1.0	Effective Date: 	Page: 13 of 35

Demographic and subject disposition characteristics will be described using frequency and percentage for categorical measures (age group, gender, race, ethnicity, highest level of education attained, and experience with laboratory and COVID-19 testing, completion of IFU [vs. discontinuation]) and mean, standard deviation, median, and interquartile range for continuous measures (age).

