#### 8.5 Handling of Missing Data

Missing data will not be imputed. All percentages will be out of the number of non-missing responses, unless otherwise specified. Per the published scoring guidelines for the ASQ, the overall score is calculated by taking the average of the non-missing items.

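### Tables 8 and 9 exclude any subject with one 'not applicable' task code, so recorded failures and some complete critical-task totals leave the per-subject summary

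*SAP*

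**What the plan says.** SAP 7.2.1 has the observer choose one of four codes for each of 26 IFU steps. The last two codes are "subject did not complete step or required assistance; or, not applicable", and the example given for the final one is "e.g., if the subject discontinued their participation".

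SAP 7.5.2.3.1 and 7.5.2.3.2 build per-subject endpoints from these codes. The second is "The total number of critical tasks that the subject does not complete". Neither definition mentions an exclusion.

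SAP 8.2.3.1 adds one for both totals: "This will be presented for the subset of patients for whom the observer was able to observe the subject attempt all tasks". It then states that subjects with a 'not applicable' response "to one or more tasks will not contribute to this analysis". In Appendix II, the first row of the Table 9 shell has the same wording as in Table 8 and counts subjects with all tasks observed, although Table 9 concerns only the 15 critical tasks.

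Other outputs carry no such exclusion. SAP 8.2.3.2 and Table 10 report every code for every task, with a column for 'not applicable'. Listings 1 to 26 give each subject's code. Table 14 reports completion or discontinuation of the IFU. Protocol 7.3 says that data available up to withdrawal are collected.

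**The concern.** Two separate things go wrong in the per-subject totals.

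First, a subject may stop because the instructions could not be followed. Exclusion then depends on the outcome being counted, and codes recorded before the stop disappear from both tables.

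Second, Table 9 can discard complete data. A subject with all 15 critical tasks observed is left out if one non-critical task is coded 'not applicable'. Comparability of totals cannot justify that, because the critical-task total is complete.

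At stake is a simple question: how many enrolled subjects failed at least one critical step? Protocol 6.2 treats failure of a critical task as a use error or performance failure, finding such problems is a secondary objective, and the study report is to accompany a regulatory filing (SAP 2).

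**Working it through.** **1. Task counts.** SAP 7.2.1 lists 1 + 2 = 3 steps before collection, 2 + 2 + 4 + 2 + 2 + 2 + 2 + 1 + 3 = 20 for collection and 1 + 2 = 3 for shipping. That gives 3 + 20 + 3 = 26, as stated. Table 10 flags 1.1, 2.1, 2.2, 2.5, 2.9 to 2.13, 2.15 to 2.17, 2.19, 3.2 and 3.3 as critical, which is 15, as stated. The other 26 − 15 = 11 are non-critical.

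**2. Subject who stops partway.** A subject who stops after 2.10 has 13 tasks observed, 6 of them critical (1.1, 2.1, 2.2, 2.5, 2.9, 2.10). Any failure among them is absent from Tables 8 and 9. The last task, 3.3, is critical, so a stop before the end always leaves the critical total incomplete. Changing Table 9 eligibility to the 15 critical tasks would not bring this subject back.

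**3. Isolated code on a non-critical task.** Here the critical total is complete but the subject still leaves Table 9. If such codes arise independently at an assumed rate q per task, expected exclusions among 30 subjects are 30 × (1 − (1 − q)^26) under the present rule and 30 × (1 − (1 − q)^15) under a critical-tasks rule. For q = 0.5% this is 3.7 against 2.2; for q = 1% it is 6.9 against 4.2.

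**4. Effect on the share with a critical failure.** Take the 30 subjects targeted. Let x be fully observed subjects with a critical failure and m be subjects excluded. Both are assumed. Table 9 shows x/(30 − m). The all-enrolled share with an observed critical failure lies between x/30 (no excluded subject had one) and (x + m)/30 (all did).

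| x | m | Table 9 | All-enrolled range |
|---|---|---|---|
| 0 | 0 | 0/30 = 0% | 0% |
| 0 | 1 | 0/29 = 0% | 0 to 3.3% |
| 0 | 3 | 0/27 = 0% | 0 to 10.0% |
| 0 | 5 | 0/25 = 0% | 0 to 16.7% |
| 3 | 0 | 3/30 = 10.0% | 10.0% |
| 3 | 1 | 3/29 = 10.3% | 10.0 to 13.3% |
| 3 | 3 | 3/27 = 11.1% | 10.0 to 20.0% |
| 3 | 5 | 3/25 = 12.0% | 10.0 to 26.7% |

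Table 9 can therefore be slightly too high or clearly too low.

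**5. Both routes together (x = 3, m = 3, assumed).** One excluded subject stopped with no observed failure. Two had 'not applicable' on a non-critical task only, and one of these failed a critical task. Table 9 shows 3/27 = 11.1%. Eligibility on the 15 critical tasks gives 4/29 = 13.8%. The all-enrolled share with an observed failure is 4/30 = 13.3%, with 1/30 = 3.3% stopped and no failure seen.

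**6. Whether other tables fill the gap.** Table 10 counts codes task by task, so one subject can appear several times. Three failures on 2.9 and three on 2.10 fit anything from 3 to 6 subjects. Table 14 gives the number discontinued, but not whether they had failed a critical task. Merging Listings 1 to 26 on subject ID would give the answer; no unredacted table does so.

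**The case against.** The rule is disclosed and has a sound reason. A total out of 26 or 15 tasks is not comparable for someone who did not attempt them all, and the first shell row reports the size of the subset. This stands for the means and distributions, which should stay as they are.

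A reader might infer that the failures are lost from the report. They are not: Table 10 and Listings 1 to 26 show them, Table 14 shows discontinuation, and the root-cause review in SAP 8.2.4 works from listings. A subject who struggles but continues with help is coded as not having completed the step and remains in both tables.

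A reader might also see a conflict with the ASQ rule in SAP 8.2.1.3, where the denominator over "responses 1 through 7, not applicable, and missing) will be the total number of enrolled patients". That rule covers item frequencies. Its counterpart for tasks is Table 10, which also shows 'not applicable', so the comparison reveals no inconsistency. Nor is the 'Enrolled' label in Appendix I a contradiction: every table listed there carries it, and it can simply name the analytic cohort.

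It is also tempting to score every stop as a critical failure. Protocol 7.3 allows withdrawal by the investigator, by the sponsor or for ineligibility, and SAP 8.5 rules out imputation. A stop without an observed failure should not be counted as one.

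Finally, the only documented use of 'not applicable' is discontinuation, so the non-critical route is possible, because that use is only an example, but not described. The second row of the Table 9 shell also omits the word critical, so a programmer might read its first row as meaning critical tasks. SAP 8.2.3.1 makes no such distinction, and the wording should settle it.

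**Conclusion.** The point holds as a minor one. The exclusion removes recorded failures from the totals in Tables 8 and 9, and as written it can remove complete critical-task totals from Table 9. No visible table gives the number of enrolled subjects with at least one observed critical-task failure.

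Size and direction cannot be determined. The documents give no rate of 'not applicable' codes or of discontinuation, the visit lasts up to one day, and the effect is zero if no such code occurs. With 30 subjects, each one excluded widens the possible range by 1/30 = 3.3 percentage points. The claim that Table 9 understates failure is not supported as a general statement; it holds only if excluded subjects fail more often than those retained. The tables are secondary and descriptive with no acceptance threshold, and the primary endpoint is unaffected.

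**What to change.** 1. Base Table 9 eligibility on the 15 critical tasks, in SAP 8.2.3.1 and in the first row of the shell.
2. Add one block to Table 9 with all enrolled subjects as denominator, as n (%) in four exclusive categories:
   - at least one observed code of not completed on a critical task;
   - all 15 critical tasks observed and none failed;
   - no observed critical failure, but stopped before finishing the IFU;
   - no observed critical failure, but one or more critical tasks 'not applicable' for another reason, or IFU not started.

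   State the denominator explicitly, because SAP 8.5 says "All percentages will be out of the number of non-missing responses, unless otherwise specified". A count that scores stops as failures may be added as a labelled sensitivity analysis.
3. Keep the present means and distributions, labelled as the all-tasks-observed subset in Table 8 and the all-critical-tasks-observed subset in Table 9, with the number excluded. Footnote the subset against the 'Enrolled' label in Appendix I.

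The cost is SAP wording, two table shells and one derived variable, with no new data collection. The reason for a 'not applicable' code must be classified from the observer's notes, preferably before test results are linked. The figures may look less favourable.
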